**Table 9 : Hematological criteria for dose modification/interruption of regorafenib**

Grade a	ANC ( $10^9/L$ )	Platelets ( $10^9/L$ )	Dose interruption	Dose modification
0-2	>1.0	$\geq$ 50	No interruption of therapy	No change
3	<1.0 – 0.5	<50 – 25	Interrupt therapy until toxicity resolves to Grade $\leq$ 2 b	1 st and 2 nd occurrence: no change 3 rd occurrence : Decrease dose by 40 mg (one tablet)
4	<0.5	<25	Interrupt therapy until toxicity resolves to Grade $\leq$ 2 b	1 st and 2 nd occurrence: no change 3 rd occurrence : Decrease dose by 80 mg (two tablets)

a Applies to all hematological toxicities; absolute neutrophil count (ANC) and platelet count displayed as examples.

b If no recovery after 28 day interruption, treatment will be discontinued

◦ Dose will not be re-escalated to original dose level after reduction for toxicity. If more than 2 dose reduction steps are required, treatment will be discontinued

Dose modifications required for study drug-related increases in ALT and/or AST levels and requirements for monitoring are provided in Table 10. During the first 3 cycles of treatment, ALT, AST, and bilirubin must be obtained at baseline and monitored weekly, even if values are normal.

**Table 10 : Dose modifications in case of drug-related liver function test abnormalities**

Observed elevations of ALT and/or AST	Occurrence	Recommended measures and dose modification
≤5 times upper limit of normal (ULN) (maximum Grade 2)	Any occurrence	Continue regorafenib treatment. Monitor liver function weekly until transaminases return to < 3 times ULN (Grade 1) or baseline.
> 5 times ULN ≤ 20 times ULN (Grade 3)	1st occurrence	Interrupt regorafenib treatment. Monitor transaminases weekly until return to < 3 times ULN or baseline. Restart: If the potential benefit outweighs the risk of hepatotoxicity, re-start regorafenib treatment, reduce dose by 40 mg (one tablet), and monitor liver function weekly for at least 4 weeks.
	Re-occurrence	Discontinue treatment with regorafenib permanently.
>20 times ULN (Grade 4)	Any occurrence	Discontinue treatment with regorafenib permanently.
>3 times ULN (Grade 2 or higher) with concurrent bilirubin >2 times ULN	Any occurrence	Discontinue treatment with regorafenib permanently. Monitor liver function weekly until resolution or return to baseline. Exception: patients with Gilbert's syndrome who develop elevated transaminases should be managed as per the above outlined recommendations for the respective observed elevation of ALT and/or AST.

Dose modifications and measures in case of hand-foot skin reaction (HFSR)/palmar-plantar erythrodysesthesia syndrome are provided in Table 11.

**Table 11 : Dose modifications and measures for HFSR**

Skin toxicity grade	Occurrence	Recommended dose modification and measures
Grade 1	Any	Maintain dose level and immediately institute supportive measures for symptomatic relief.
Grade 2	1st occurrence	Decrease dose by 40 mg (one tablet) and institute supportive measures. If no improvement occurs despite dose reduction, interrupt therapy for a minimum of 7 days, until toxicity resolves to Grade 0-1. A dose re-escalation is permitted at the discretion of the investigator.
	No improvement within 7 days or 2nd occurrence	Interrupt therapy until toxicity resolves to Grade 0-1. When re-starting treatment, decrease dose by 40 mg (one tablet). A dose re-escalation is permitted at the discretion of the investigator.
	3rd occurrence	Interrupt therapy until toxicity resolves to Grade 0-1. When re-starting treatment, decrease dose by 40 mg (one tablet). A dose re-escalation is permitted at the discretion of the investigator.
	4th occurrence	Discontinue treatment with regorafenib permanently.
Grade 3	1st occurrence	Institute supportive measures immediately. Interrupt therapy for a minimum of 7 days until toxicity resolves to Grade 0-1. When re-starting treatment, decrease dose by 40 mg (one tablet). A dose re-escalation is permitted at the discretion of the investigator.
	2nd occurrence	Institute supportive measures immediately. Interrupt therapy for a minimum of 7 days until toxicity resolves to Grade 0-1. When re-starting treatment, decrease dose by 40 mg (one tablet).
	3rd occurrence	Discontinue treatment with regorafenib permanently.

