## Phase I

DLT monitoring must be performed during the first three cycles of treatment. Patients will be treated until disease progression.

In case of patient withdrawal before completing the entire third cycle for reasons other than DLT, a new patient will be included at this dose level.

The phase I part of this study will be designed as a standard 3+3 design for dose escalation/de-escalation and 3 to 6 patients will be enrolled in each cohort sequentially, depending on occurrence of dose limiting toxicities (Figure 1).

A standard 3 + 3 design will be followed in the dose escalation part of study.

Three dose levels for Irinotecan/Regorafenib (IRI 150/REGO 120, IRI 180/REGO 120, IRI 180/REGO 160) are planned as well as a -1 level (IRI 150/REGO 80) to be opened in case of maximum tolerated dose (MTD) was reached at level 1 (Table 1).

Table 1 :

Steps	Dose Levels	Number of patients
DL-1	IRI 150/REGO 80	0-6
DL1	IRI 150/REGO 120	3-6
DL2	IRI 180/REGO 120	3-6
DL3	IRI 180/REGO 160	3-6

At each dose level, three patients will be included. Three additional patients will be enrolled at the same dose level if one dose limiting toxicity (DLT) is observed in the first three patients of this dose level (Figure 1).

Figure 1 :

[figure not shown]

Table 2 : Dose escalation rules

Outcome (# DLT / # Patients)	Action
0 DLT out of the first 3 patients	Include 3 patients at the next dose level
1 DLT out of 3 patients	Include 3 additional patients at the same dose level.
$\geq 2$ DLT out of 3 patients	Stop dose escalation. Include 3 additional patients at the previous dose level (unless 6 subjects were already treated).
$\geq 2$ DLT out of 6 patients	Stop dose escalation. Include 3 additional patients at the previous dose level (unless 6 patients were already treated).

The MTD is defined as the dose at which at least two out of three to six patients experienced a DLT during the first three cycles of treatment.

Dose escalation will be stopped if MTD is reached or the last dose level (IRI 180/REGO 160) is reached (MTD not reached).

The recommended phase II dose (RP2D) is defined as the dose closest to the MTD at which a DLT is observed in 0/3 or 1/6 patients.

Should any patient discontinue the study prior to completing the entire (3 cycles) for reasons other than a DLT then a replacement patient will be added at that dose level.

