## **Regorafenib**

For List of excipients and Storage: See Investigator's brochure (appendix 7).

The investigational drug regorafenib must be exclusively used for the investigation specified in this protocol, and it will only be accessible to authorized staff. The sponsor delegate labelling, packaging and shipping of product during the study to Sodia. Sodia will perform this prestation in accordance with applicable Good Manufacturing Practices.

Regorafenib will be provided by Sponsor as film-coated tablets of 40 mg in 30-tablet bottles.

The investigational product(s) label will bear sponsor's name, address and telephone number, the EudraCT number, product name, dosage form and strength, batch number, expiration date, required storage conditions and required caution statements as applicable.

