**Table 12 : Dose modification/interruption and management of treatment-emergent hypertension**

Severity grade	Definition	Antihypertensive therapy	Dose modification/interruption
Grade 1	Prehypertension: SBP 120-139 mmHg or DBP 80-89 mmHg	None	Continue study drug. Consider increased BP monitoring
Grade 2	SBP 140-159 mmHg or DBP 90-99 mmHg or symptomatic increase in DBP >20 mmHg or to >140/90 mmHg if previously within normal limits	Treat with the aim to achieve DBP $\leq$ 90 mmHg. If S/DBP previously within normal limits, start antihypertensive monotherapy. If subject is taking antihypertensive medication, titrate the dosage up.	Continue study drug. If symptomatic, delay dose until symptoms resolve AND diastolic BP $\leq$ 90 mmHg Restart dose at same dose level.
Grade 3	SBP $\geq$ 160 mmHg or DBP $\geq$ 100 mmHg or $\geq$ 1 antihypertensive drug or more intensive antihypertensive therapy required than previously	Treat to DBP $\leq$ 90 mmHg. Start antihypertensive medication. and/or Increase dose of current antihypertensive medication. and/or add additional antihypertensive medication(s)	Delay dose until DBP $\leq$ 90 mmHg and, if symptomatic, until symptoms resolve. A restart dose will be at the same dose level. If BP not controlled with more intensive therapy, reduce dose to Dose reduction step -1 If Grade 3 hypertension recurs after dose reduction and antihypertensive therapy, reduce dose to Dose reduction step -2
Grade 4	Life-threatening consequences (malignant hypertension): transient or permanent neurologic deficit, hypertensive crisis	--	Discontinue therapy

In cases only one value is >Grade 1 (e.g., 155/88 mmHg), the guidelines provided for the highest grade should be followed. Patients requiring interruption of study treatment > 4 consecutive weeks must discontinue study drug.

If BP remains controlled for  $\geq$  one full cycle, dose re-escalation is permitted at the investigator's discretion

Blood pressure will be recorded by the treating physician and entered onto the e-CRF.

Any blood pressure that is out of normal range must be reported to the treating physician.

Blood pressure measurements considered out of normal range are diastolic  $\geq 100$  mmHg and systolic  $\geq 150$  mmHg, or a  $\geq 20$  mmHg increase in diastolic measurement if the measurement was previously within normal limits.

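### The regorafenib reduction rules in section 6.6 are not adapted to the 80 mg and 120 mg starting doses: some sequences instruct a restart at 0 mg, and the reach of the two-step limit is unclear

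*Combined protocol and SAP*

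**What the plan says.** Section 3.1 (Phase I, Table 1) sets the starting doses: "Three dose levels for Irinotecan/Regorafenib (IRI 150/REGO 120, IRI 180/REGO 120, IRI 180/REGO 160) are planned". A fourth, lower level with regorafenib 80 mg is contingent: it is used only if level 1 turns out to be the MTD. Section 6.2 supplies regorafenib as "film-coated tablets of 40 mg in 30-tablet bottles", so 40 mg is the smallest step that whole tablets allow.

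Section 6.6 then gives the regorafenib reductions by type of toxicity:

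- **Table 11 (HFSR).** Grade 2: a 40 mg decrease at the 1st, 2nd and 3rd occurrence, permanent stop at the 4th. Grade 3: a 40 mg decrease at the 1st and 2nd occurrence, permanent stop at the 3rd. The wording for grade 2 occurrences 2 and 3, and for both grade 3 decreases, is "When re-starting treatment, decrease dose by 40 mg (one tablet". Re-escalation is left to the investigator at grade 2 occurrences 1 to 3 and at the 1st grade 3 occurrence. It is not offered at the 2nd grade 3 occurrence.
- **Table 9 (haematological).** No change at the first two occurrences. At the 3rd, grade 3 takes off 40 mg and grade 4 reads "Decrease dose by 80 mg (two tablets". A note below the table bars a return to the original dose level and adds: "If more than 2 dose reduction steps are required, treatment will be discontinued".
- **Table 12 (hypertension).** Names two steps, the second as "reduce dose to Dose reduction step -2", with no mg value for either.
- **Tables 8 and 10.** Table 8 takes off 40 mg for a grade 3 or 4 event and states no cap. Table 10 allows one 40 mg reduction and then a permanent stop.

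No table is indexed by starting dose, and no lowest regorafenib dose is stated.

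**The concern.** The number of 40 mg steps available depends on the starting dose: four tablets at 160 mg, three at 120 mg, two at 80 mg. Table 11's grade 2 sequence uses three before the stop row, which fits only a 160 mg start. Two of the three planned levels start at 120 mg, and the contingent level starts at 80 mg, so the recommended phase II dose could be one of these.

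Where the text says to restart and the subtraction leaves nothing, sites have to improvise. One may stop permanently, another hold and re-escalate, another stay at 40 mg. Regorafenib exposure and the recorded date and reason of discontinuation would then differ between sites for the same event.

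The sequences are foreseeable. The background section reports 15% grade 3-4 HFSR in an earlier study of regorafenib 160 mg with FOLFOX or FOLFIRI. Under section 6.4, non-progressing patients who remain unresectable go on to regorafenib maintenance after 12 cycles (12 x 14 days = 168 days = 24 weeks if consecutive), so occurrences can accumulate over a long period.

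**Working it through.** The plan states no figure to reproduce. The check subtracts each table's decreases in order from each starting dose, without re-escalation.

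**Inputs.** Starting doses 160, 120 and 80 mg (section 3.1, Table 1); 40 mg tablets (section 6.2); decreases from Tables 8 to 12 (section 6.6). Assumption: one Table 12 step is 40 mg, because the protocol gives no value.

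**Formula.** Dose after k decreases = starting dose minus the sum of the first k decreases.

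| Rule | From 160 mg | From 120 mg | From 80 mg |
|---|---|---|---|
| Table 11, grade 2, occurrences 1-3 (40 each) | 120, 80, 40 | 80, 40, **0** | 40, **0** (2nd) |
| Table 11, grade 3, occurrences 1-2 (40 each) | 120, 80 | 80, 40 | 40, **0** |
| Table 9, grade 3, 3rd occurrence (40) | 120 | 80 | 40 |
| Table 9, grade 4, 3rd occurrence (80) | 80 | 40 | **0** |
| Table 10, grade 3, 1st occurrence (40) | 120 | 80 | 40 |
| Table 12, steps -1 and -2 (40 each, assumed) | 120, 80 | 80, 40 | 40, **0** |
| Table 8, repeated 40 mg decreases (no cap stated) | 120, 80, 40 | 80, 40, **0** | 40, **0** (2nd) |

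**Where 0 mg comes before the stop row in Table 11.**
- From 120 mg, grade 2: 120 - 3 x 40 = 0 at the 3rd occurrence; the stop is at the 4th.
- From 80 mg, grade 2: 80 - 2 x 40 = 0 at the 2nd occurrence; the stop is at the 4th.
- From 80 mg, grade 3: 80 - 2 x 40 = 0 at the 2nd occurrence; the stop is at the 3rd.
- From 160 mg, grade 2: 160 - 3 x 40 = 40, so the sequence fits. Zero is reached only if the lack-of-improvement condition is counted as a separate fourth decrease (160 - 4 x 40 = 0).

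**Does the two-step limit under Table 9 resolve this?** Take each reading in turn.
1. *It covers Table 9 only.* Different limits for different toxicities are then no contradiction, but Table 11 has no limit short of its stop row and runs to 0 mg from 120 mg.
2. *It covers all regorafenib reductions.* Treatment would stop after 120 > 80 > 40, so 0 mg is not reached from 120 mg by 40 mg steps. But Table 11 orders a third reduction where the limit orders discontinuation. The bar on returning to the original dose also conflicts with Tables 8, 11 and 12, where re-escalating by one step after a single reduction is exactly such a return.
3. *From 80 mg, either reading.* Two 40 mg steps give 80 - 2 x 40 = 0 without exceeding two steps. The limit does not prevent 0 mg.

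**Extent.** Three of the four dose levels, or two of the three distinct regorafenib doses, have at least one path to 0 mg.

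**The case against.** The strongest case against is that the problem is confined to the end of a few sequences, and most of that stands.

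- The first 40 mg reduction works at every level and the first two work at 120 mg. From 120 mg, Table 10, Table 11 grade 3, either row of Table 9 taken alone, and Table 12 on the 40 mg assumption all end above 0 mg.
- A reader might infer that the rules cannot be followed at most of the trial's doses. The documents do not support that: the failures are late steps, and for grade 2 HFSR they assume that no re-escalation was used.
- A reader might infer that one grade 4 haematological event removes the whole 80 mg dose. Table 9 makes no change at the first two occurrences; the 80 mg cut comes at the 3rd.
- The 80 mg level opens only if the MTD is reached at level 1, and it may never be used.
- A reader might infer a flat contradiction between Tables 9 and 11 on the number of reductions. That depends on the reach of the note, whose marker has no matching reference in the extracted text. At 120 mg, Table 11's 0 mg result and the conflict over the limit do not arise on the same reading.
- Section 9.1 lists adverse events that dose modification cannot manage, and interruptions beyond 28 days, as possible reasons to discontinue, so a patient with no lower dose is not left without any rule.
- A reader might infer an effect on the DLT assessment or the 48-week endpoint. The DLT window holds 3 x 7 = 21 regorafenib days, which leaves little room for three separate occurrences. The endpoint counts progression or death, and stopping treatment is not withdrawal from the trial. No effect size can be derived.

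What these points do not remove: re-escalation is optional, and a rule must also work when the option is not used; section 9.1 does not change the restart wording in Table 11; and neither reading of the note makes the text consistent at both 80 and 120 mg.

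**Conclusion.** The point holds in a limited form. Section 6.6 was not adapted to starting doses below 160 mg. Table 11 as written instructs a restart at 0 mg at the 3rd grade 2 HFSR occurrence from 120 mg, and at the 2nd grade 2 or grade 3 occurrence from 80 mg, while placing the permanent stop later. Table 9's decrease at the 3rd grade 4 occurrence equals the full dose of the contingent level ("IRI 150/REGO 80"). The scope of the two-step limit and of the re-escalation bar is not clear, and Table 12's steps have no dose.

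The Table 11 result assumes no re-escalation; it needs no assumption about step size, since the tables give the 40 mg. Only the Table 12 row rests on an assumed 40 mg step. The consequence is non-uniform handling of late reductions, and so of exposure and discontinuation data, with a bearing on patient safety. It is worth correcting because stated rules become unworkable, not because a bias in the primary endpoint has been shown.

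**What to change.** Amend the wording of section 6.6:

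1. Reconcile Tables 8 to 12 with the starting doses in Table 1, so that no sequence instructs a restart at 0 mg.
2. State which toxicities the two-step limit and the bar on returning to the original dose cover, and bring the third reduction in Table 11 and the re-escalation text in Tables 8, 11 and 12 into line with that statement.
3. Give the dose meant by steps -1 and -2 in Table 12 for each starting dose.

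Which doses, steps and stopping rules apply is a decision for the sponsor and its clinical team. The cost is protocol wording, handled through the amendment procedure in section 13.6. Sample size and analysis are not affected.

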## Suggestions:

### **Control of calluses**

Before initiating treatment with regorafenib:

- Check condition of hands and feet
- Suggest a manicure/pedicure, when indicated

- Recommend pumice stone use for callus or 'rough spot' removal.

During regorafenib treatment:

- Avoid pressure points
- Avoid items that rub, pinch or create friction

### Use of creams

Apply non-urea based creams liberally, e.g.,

- Cetaphil
- Aveeno
- Norwegian Formula
- Eucerin

Keratolytic Creams: Use sparingly and only to affected (hyperkeratotic) areas

- Urea-based creams
- Salicylic acid 6%

Alpha Hydroxy Acids (AHA) based creams

- Approximately 5-8% provide gentle chemical exfoliation
- Apply liberally two times each day

Topical analgesics like lidocaine 2% to be considered for pain control

Topical corticosteroids should be considered for subjects with Grade 2 or 3 hand-foot skin reaction. Avoid systemic steroids.

### Cushions

Protect tender areas

- Use socks/gloves to cover moisturizing creams
- Wear well-padded footwear
- Use insole cushions or inserts (e.g., silicon, gel)

- Foot soaks with tepid water and Epsom salts

**Table 12 : Dose modification/interruption and management of treatment-emergent hypertension**

Severity grade	Definition	Antihypertensive therapy	Dose modification/interruption
Grade 1	Prehypertension: SBP 120-139 mmHg or DBP 80-89 mmHg	None	Continue study drug. Consider increased BP monitoring
Grade 2	SBP 140-159 mmHg or DBP 90-99 mmHg or symptomatic increase in DBP >20 mmHg or to >140/90 mmHg if previously within normal limits	Treat with the aim to achieve DBP $\leq$ 90 mmHg. If S/DBP previously within normal limits, start antihypertensive monotherapy. If subject is taking antihypertensive medication, titrate the dosage up.	Continue study drug. If symptomatic, delay dose until symptoms resolve AND diastolic BP $\leq$ 90 mmHg Restart dose at same dose level.
Grade 3	SBP $\geq$ 160 mmHg or DBP $\geq$ 100 mmHg or $\geq$ 1 antihypertensive drug or more intensive antihypertensive therapy required than previously	Treat to DBP $\leq$ 90 mmHg. Start antihypertensive medication. and/or Increase dose of current antihypertensive medication. and/or add additional antihypertensive medication(s)	Delay dose until DBP $\leq$ 90 mmHg and, if symptomatic, until symptoms resolve. A restart dose will be at the same dose level. If BP not controlled with more intensive therapy, reduce dose to Dose reduction step -1 If Grade 3 hypertension recurs after dose reduction and antihypertensive therapy, reduce dose to Dose reduction step -2
Grade 4	Life-threatening consequences (malignant hypertension): transient or permanent neurologic deficit, hypertensive crisis	--	Discontinue therapy

In cases only one value is >Grade 1 (e.g., 155/88 mmHg), the guidelines provided for the highest grade should be followed. Patients requiring interruption of study treatment > 4 consecutive weeks must discontinue study drug.

If BP remains controlled for  $\geq$  one full cycle, dose re-escalation is permitted at the investigator's discretion

Blood pressure will be recorded by the treating physician and entered onto the e-CRF.

Any blood pressure that is out of normal range must be reported to the treating physician.

Blood pressure measurements considered out of normal range are diastolic  $\geq 100$  mmHg and systolic  $\geq 150$  mmHg, or a  $\geq 20$  mmHg increase in diastolic measurement if the measurement was previously within normal limits.

The dose modification schedule for treatment emergent hypertension during regorafenib dosing should be followed (see [Table 12]). Patients' blood pressure (BP) measurements will be monitored and appropriate treatment to effectively control hypertension under regorafenib treatment is strongly recommended.

The selection of anti-hypertensive medication used in this setting should be performed at the investigator's discretion, considering possible site-specific treatment guidelines. All medication should be recorded in the subjects e-CRF.

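### Table 12 lets regorafenib restart after grade 3 hypertension on diastolic pressure alone, so isolated systolic grade 3 triggers no effective hold

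*Combined protocol and SAP*

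**What the plan says.** Section 6.6, Table 12, sets out how regorafenib is managed in treatment-emergent hypertension.

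- **Grade 3 definition.** Any one of three limbs is enough: SBP ≥ 160 mmHg, DBP ≥ 100 mmHg, or a need for antihypertensive drug treatment or for more intensive treatment than before.
- **Grade 3 treatment aim.** DBP ≤ 90 mmHg. No systolic value is given.
- **Grade 3 action.** The cell opens "Delay dose until DBP" and sets the limit at ≤ "90 mmHg and, if symptomatic, until symptoms resolve. A restart dose will be at the same dose level". It continues: "If BP not controlled with more intensive therapy, reduce dose to Dose reduction step -1".
- **One raised value.** The note under the table reads: "In cases only one value is >Grade 1 (e.g., 155/88 mmHg), the guidelines provided for the highest grade should be followed". A patient whose SBP alone is in the grade 3 range is therefore managed under the grade 3 row.
- **Grade 2, for comparison.** Asymptomatic patients stay on drug. The aim is again diastolic only: "Treat with the aim to achieve DBP" ≤ 90 mmHg.
- **Long interruptions.** "Patients requiring interruption of study treatment > 4 consecutive weeks must discontinue study drug".

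**The concern.** The grade is assigned on either pressure, but the hold is lifted on one of them. When systolic pressure alone drives the grade and DBP is already at or below 90, an asymptomatic patient has nothing to wait for. The table orders a delay that ends as it begins.

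What is at stake is patient safety in a small subset. Someone with SBP at or above 160 could take the next tablet at an unchanged dose before the new or increased antihypertensive drug has worked. The rule also treats two patients of the same grade differently according to which pressure put them there.

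**Working it through.** No sample size, power or error rate is involved, so the check applies the table's conditions to readings and then looks for a systolic limit elsewhere.

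**Inputs (Table 12).** Pressure limbs of grade 3: SBP ≥ 160 or DBP ≥ 100. Pressure condition for restart: DBP ≤ 90. Symptom condition: only if symptomatic.

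**Step 1. Apply the rule to illustrative asymptomatic readings.**

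| Reading | Grade 3 by SBP? | Grade 3 by DBP? | DBP ≤ 90? | Result |
|---|---|---|---|---|
| 175/85 | yes (175 ≥ 160) | no | yes (85) | restart condition met at onset |
| 165/105 | yes (165 ≥ 160) | yes (105 ≥ 100) | no | held |
| 165/90, the same patient later | yes (165 ≥ 160) | no | yes (90) | restart condition met, still grade 3 by SBP |
| 170/95 | yes (170 ≥ 160) | no | no (95) | held until DBP falls to 90 |
| 150/100 | no | yes (100 ≥ 100) | no | held until DBP falls to 90 |

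The first and third rows show the gap. The fourth and fifth show that the hold works when DBP is above 90. A symptomatic patient is held in every case until symptoms resolve.

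**Step 2. Look for a systolic hold or restart limit elsewhere.**

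- Table 8 (section 6.6) interrupts other grade 3 non-hematological events until grade 2 or lower, but its title excludes hypertension.
- Non-inclusion criterion 7 (section 4.3) uses SBP > 140 or DBP > 90, but only at entry.
- The notes under Table 12 name systolic ≥ 150 in the definition of an out-of-range reading. The consequence is a report to the treating physician, not a hold.
- The text after those notes recommends effective control and gives no number.
- The termination list at the end of section 6.6 and the grade 4 row act only at severe crisis or life-threatening consequences.
- Section 9.1 lets the investigator stop treatment judged detrimental and sets no threshold.

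None of these supplies the limit.

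**Step 3. When could it matter?** Regorafenib is taken on days 4 to 10 of a 14-day cycle. Section 5.3 lists blood pressure among the first-day-of-cycle assessments, every other week for three cycles. The schedule in section 5.1 marks it on day 1 of cycles 1 to 3 and has no mark from cycle 4 until the end of treatment. A day 1 reading precedes the first tablet of the cycle by 4 − 1 = 3 days, and antihypertensive treatment should start or be intensified in that time. The gap therefore applies in two situations: SBP still ≥ 160 when dosing falls due, or a diary or unscheduled reading on days 4 to 10.

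**The case against.** The strongest reply is that the table does respond to persistent systolic pressure through the step −1 rule. Control is given no number there, nor in the re-escalation note that begins "If BP remains controlled for". The only numeric description of uncontrolled hypertension in the protocol is the entry criterion, which includes SBP > 140. On that reading, same-dose treatment at a high SBP lasts only until intensified therapy has been tried. This stands as a limit on the consequence, and it would be wrong to say that the dose stays unchanged whatever the systolic pressure does. But the rule sets the dose level and does not create a hold.

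Other protections also stand. Antihypertensive treatment is required by the grade. Out-of-range readings go to the physician, although the wording joins the diastolic and systolic values with an *and*, so its application to isolated systolic elevation is unclear. Hypertension is not among the exceptions to the grade 3 non-hematologic dose-limiting toxicity in section 2.2.1, so a drug-related event in cycles 1 to 3 still counts.

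Three stronger readings are tempting, and the documents do not support them.

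- **An exposure window of 7 days in 14.** That is the dosing window. The protocol schedules no blood pressure reading within it.
- **A measurable excess over a ceiling of 159 mmHg.** The grade 2 row ("Continue study drug. If symptomatic, delay dose until symptoms resolve AND diastolic BP") keeps asymptomatic SBP 140–159 on drug, so a reader might treat 159 as the table's own restart limit. But the table does not use its continuation range that way even for diastolic pressure: asymptomatic DBP 91–99 with SBP < 160 continues, yet a grade 3 restart needs ≤ 90. An excess in mmHg would rest on a borrowed benchmark and an invented reading.
- **That SBP < 160 would match Table 8's return to grade 2.** Grade 3 also has the therapy limb. A treated patient at 155/85 may still be grade 3 on that limb.

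**Conclusion.** The point holds in a narrow form. For an asymptomatic patient with SBP ≥ 160 and DBP ≤ 90, the grade 3 delay in Table 12 has no effect. A patient held for raised DBP may also restart while SBP is still in the grade 3 range. Nothing else in the protocol sets a systolic hold or restart limit.

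The conclusion rests on reading Table 12 literally and on the patient being free of symptoms. It does not cover DBP above 90, symptomatic patients, or grade 3 reached only through the therapy limb. The documents give no rate of grade 3 or isolated systolic hypertension, so no frequency and no size in mmHg is claimed.

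Severity is minor. This is a safety rule that gives the wrong answer when followed as written, in few foreseeable situations, with other protections in place. The phase II sample size and decision rule do not change.

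**What to change.** In the grade 3 row of Table 12, add SBP < 160 mmHg beside DBP ≤ 90 mmHg in the delay condition, and keep the symptom condition as it is. This clears the pressure limbs of grade 3 before restart; it does not address the therapy limb and need not.

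In the same row, add a systolic value to the treatment aim. The pair 140/90 from non-inclusion criterion 7 is a natural candidate, to be confirmed by the clinical team.

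The cost is a wording change in one row and a few longer holds. Rarely, one of these could reach the rule that an interruption of more than four consecutive weeks ends treatment. In phase I, a drug-related grade 3 event in cycles 1 to 3 is already a dose-limiting toxicity, so a longer hold for it adds no new one.
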